8.3. Exclusion Criteria

Subjects who meet any of the following criteria are not eligible for enrollment:

1. Participating in any other clinical trial of an investigational treatment for COVID-19
2. Methemoglobin > 3%
3. Evidence of severe multi organ failure as defined as (any one of the following):

Organ System	Severe Criteria
Hepatic	Jaundice with bilirubin 8-10 mg/DL
Renal	Dialysis or Renal Replacement Therapy
Hematologic	DIC

Organ System	Severe Criteria
Cardiovascular	Systemic hypotensive state not responsive to vasopressors
CNS	Coma

4. Use of assisted ventilation prior to initiation of INOpulse such as:
 - Any system of Non Invasive Ventilation (NIV), with Positive End-Expiratory Pressure (PEEP) (eg, high flow nasal cannula, CPAP [unless used for OSA] or, BiPAP) or mechanical ventilation
5. Pregnancy, or positive pregnancy test in a pre-dose examination
6. Open tracheostomy
7. Clinical contra-indication, as deemed by the Investigator
8. Chronic use of a nitric oxide donor agent such as nitroglycerin or drugs known to increase methemoglobin such as lidocaine, prilocaine, benzocaine nitroprusside, isosorbide or dapsone at screening
9. Known history or clinical evidence of systolic heart failure, left ventricular dysfunction (LVEF < 40 %)
10. Subjects reporting massive hemoptysis associated with the current illness or with radiologically proven pulmonary embolus

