COVID-19 infection must be confirmed via positive RT-PCR, or have high index of suspicion of infection with results pending. Upon successful completion of screening, subjects will receive treatment with placebo or iNO 125 mcg/kg IBW/hr up until resolution of hypoxemia, protocol defined respiratory failure, hospital discharge or Day 28, whichever occurs first. In instances where continuous INOpulse dosing is not feasible (eg, due to PPE limitations), INOpulse should be used a minimum of 12 hours daily.

Prior to randomization, the following screening assessments (0 to -14 days prior to randomization) will be completed as described in **Table 2**:

- Informed consent
- COVID-19 RT-PCR obtained from an upper respiratory tract specimen within the previous 4 days. Subjects may be positive for COVID-19 or have high suspicion of infection at the time of randomization with RT-PCR results pending. If a subject is randomized based upon a high suspicion of COVID-19 infection and the swab RT-PCR comes back negative, a repeat RT-PCR swab can be taken and the subject can be continued on INOpulse pending the repeat results. If the repeat RT-PCR results come back negative, the subject should be discontinued from INOpulse therapy. If the subject deteriorates after discontinuation of INOpulse, the Investigator should consider the reintroduction of INOpulse therapy.
- CT scan or chest x-ray after onset of symptoms and within 14 days of randomization
- CBC with differential, chemistry panel (sodium, potassium, chloride, CO₂, BUN, creatinine, glucose), LFTs (AST/ALT and total bilirubin), triglycerides, troponin (High Sensitivity Cardiac Troponin [HS-cTN]), procalcitonin, ferritin, fibrinogen, D-dimer NT-proBNP and LDH. If available locally, CRP, Von Willebrands Factor, Factor VIII Activity, Protein C, Protein S, Homocysteine, Antithrombin 3, Thrombelastography (TEG), G6PD deficiency and Prothrombin gene G2021A. Lab results obtained within the previous 48 hours are acceptable for screening purposes if there has not been a significant change in the subject's clinical status.
- Pregnancy test (urine or serum) for women of child-bearing potential
- Vital signs (heart rate, respiratory rate, blood pressure, temperature)
- Oxygen saturations
- Document oxygen flow requirements
- Medical History including a documented reason for hospital admission
- Physical exam
- Review inclusion and exclusion eligibility criteria

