11.4 Per Protocol Analysis Set

The Per-Protocol Analysis Set (PPAS) is a subset of FES, to be used for secondary analysis of efficacy. FES subjects with at least one of the following protocol deviations will be excluded from the PPAS:

- Subject did not meet all protocol-specified inclusion criteria or met at least one of the protocol-specified exclusion criteria.
- Subject received study drug other than the one that he/she was randomized to receive
- Subjects with any other protocol deviation identified in the course of study monitoring which, in the opinion of the Sponsor's Responsible Medical Officers based on blinded review, is likely to impact the validity of the data

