13.4 Important Protocol Deviations

A by-subject listing of randomized subjects with any eligibility criteria violations will be provided.

The number and percentage of randomized subjects with any important protocol deviation and the number and percentage of subjects with any important protocol deviation by deviation category will be summarized overall and by treatment group. A by-subject listing of all protocol deviations will be provided with columns identifying the date of the deviation, importance (important or not important), deviation category, and the standardized and verbatim descriptions of the deviation. All important protocol deviations will be summarized by using the FES.

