13.5 Efficacy Analyses

The primary efficacy endpoint for this study is the proportion of subjects who died or had respiratory failure (DRF) through Day 28.

All subjects in the ARAS will be included in the analysis of the efficacy endpoints. The DRF proportion will also be calculated for the following subgroups: race (White Caucasian vs African American vs Others), gender, age group (\leq 65 years vs $>$ 65 years), and baseline disease severity (oxygen \leq 5 vs $>$ 5 and comorbidities $<$ 2 or \geq 2).

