13.5.1 Estimand

The main estimand is the odds ratio for the likelihood of DRF, comparing the INOpulse group to the placebo group.

The main estimand is defined by the following attributes:

- (1) Treatment regimens for patients to be evaluated:
INOpulse at 125 micrograms/kg IBW/hr versus INOpulse placebo
- (2) Populations of patients targeted by the clinical question:
The patients targeted in this analysis are all randomized patients, grouped according to randomized treatment assignment.
- (3) Patient-level outcome to be measured:
The outcome being measured is the likelihood of death or respiratory failure at Day 28.
- (4) Intercurrent events:
The analysis will be done regardless of the use of rescue medications, protocol violations, or investigational product discontinuation. Intercurrent events which are protocol deviations will be summarized in table format. The outcome of DRF is binary, with the event being DFR, and the non-event being any other outcome. Therefore, other modifications due to intercurrent events, such as death from another cause or a subject receiving another therapy, will not be made to the outcome variable. Death will not be considered an intercurrent event for the primary endpoint as it is part of that endpoint definition. Subjects will be analyzed using an "intent to treat" approach. Sensitivity analysis of the primary outcome using the PPAS set will be conducted to evaluate the robustness of the parameter estimate.
- (5) Population-level summary measure
The population-level summary is the estimated likelihood of DFR, adjusted for treatment, baseline oxygen level (as a continuous covariate), number of co-morbidities (as a discrete numeric covariate), and age (as a continuous covariate).

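### The hepatic exclusion stops at a bilirubin of 10 mg/dL, so as written it excludes a jaundiced subject at 9 mg/dL but not one at 12 mg/dL

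*Protocol*

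**What the plan says.** Protocol section 8.3, item 3, introduces the organ-failure exclusion as "Evidence of severe multi organ failure as defined as (any one of the following" and then gives a table with one severe criterion for each of five organ systems. The hepatic entry is "Jaundice with bilirubin 8-10 mg/DL". The exclusion list in the synopsis gives the same entry in the same words, so neither place corrects the other.

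The renal, hematologic, cardiovascular and CNS rows are states that are either present or absent (dialysis, DIC, hypotension unresponsive to vasopressors, coma) and carry no number. Elsewhere in section 8.3 the numeric exclusions run in one direction only: item 2 is "Methemoglobin > 3" per cent, and item 9 sets an ejection fraction below 40%. Item 7 lets the investigator exclude for a clinical contraindication and names no laboratory level.

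The SAP takes over the protocol criteria by reference. Section 11.4 removes a subject from the Per Protocol Analysis Set (PPAS) if "Subject did not meet all protocol-specified inclusion criteria or met at least one of the protocol-specified exclusion criteria". Section 13.4 says: "A by-subject listing of randomized subjects with any eligibility criteria violations will be provided".

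**The concern.** The table is the protocol's definition of severe organ failure, and a severity criterion should not cease to apply as severity rises. The hepatic row does that at its upper end: the subject with the worse liver passes a test that the subject with the better liver fails.

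Total bilirubin is among the screening laboratory tests, and Protocol section 12.1 allows randomization only after all criteria have been met. Sites will therefore have the value in hand and a rule to apply to it. With approximately 30 sites, a rule that is silent above 10 mg/dL invites different handling of the same patient.

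Two things are at stake:

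- objective and uniform exclusion of severe hepatic failure at entry;
- correct classification of eligibility violations, which feeds the SAP 13.4 listing and PPAS membership.

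**Working it through.** No power, sample size or alpha figure is involved, so the check is one of logic and text.

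**Inputs**

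- Hepatic row, Protocol 8.3 item 3 and synopsis: jaundice with bilirubin from 8 to 10 mg/dL.
- Combination rule, same item: any one row is enough to exclude.
- Item 7, Protocol 8.3: investigator discretion, no bilirubin level.
- Total bilirubin measured at screening: synopsis screening list, Table 2 (footnote 6) and section 10.1.13.

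**Step 1: apply the row literally.** The rule is jaundice AND 8 ≤ bilirubin ≤ 10 mg/dL. For a jaundiced subject:

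| Bilirubin (mg/dL) | Meets the row as written | Meets the row if written as ≥ 8 |
|---|---|---|
| 7.9 | No | No |
| 8 | Yes | Yes |
| 9 | Yes | Yes |
| 10 | Yes | Yes |
| 10.1 | No | Yes |
| 12 | No | Yes |
| 20 | No | Yes |

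As written, the answer goes from no to yes and back to no as bilirubin rises. A floor alone changes once and stays changed.

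**Step 2: look for another rule that covers values above 10 mg/dL.** No other exclusion, and no other part of either document, sets a bilirubin threshold for entry. The other four organ rows need a different organ to have failed. Item 7 permits exclusion but does not require it.

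**Step 3: follow the wording into the SAP.** Suppose two jaundiced subjects are enrolled in error, one at 9 and one at 12 mg/dL, with no other exclusion met. The first has met an exclusion criterion, so that subject appears in the SAP 13.4 listing and leaves the PPAS under SAP 11.4. The second has not met this row, so that subject is not listed on this ground and stays in the PPAS. The PPAS supports the sensitivity analysis of the primary outcome (SAP 13.5.1 and 13.5.4).

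**Step 4: check the primary analysis.** SAP 13.5 states "All subjects in the ARAS will be included in the analysis of the efficacy endpoints", where ARAS is the All Randomized Analysis Set. SAP 13.5.1 adds "The analysis will be done regardless of the use of rescue medications, protocol violations, or investigational product discontinuation". Neither subject would be dropped from the primary analysis, so the planned 500 subjects and the 93% power do not depend on how the row is read.

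**The case against.** The strongest reply is that the context settles the meaning. The row sits in a table of severe criteria under a stem about severe organ failure. A clinician would have to accept that 9 mg/dL is severe and 12 mg/dL is not, which nobody would defend. Sites would probably read the row as at least 8 mg/dL. Where one did not, item 7 would still let the investigator exclude the patient. To be enrolled through this gap, a subject would have to be jaundiced above 10 mg/dL, need no more than 10 L/min of oxygen without assisted ventilation, meet no other organ row and be accepted by the investigator. Nothing in the documents ties such a bilirubin to harm from inhaled nitric oxide. The methemoglobin limit is also an imperfect comparator, because it relates to the study drug and is not a grade of organ failure.

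Most of this is fair, and it keeps the point minor. The likely intent, the rarity and the absence of a demonstrated safety effect all stand, and the case does not need the methemoglobin comparison. None of it supplies the missing rule. Eligibility and deviations are judged against the text, and item 7 is discretionary. If everyone agrees that the intended rule is a floor, the text should state one.

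**Conclusion.** The hepatic row is wrong as written. It is a closed range where a severity exclusion needs a floor only, and no other provision excludes a jaundiced subject above 10 mg/dL on bilirubin.

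The size is small: one boundary in one of five organ rows, stated in two places. Few subjects are likely to be affected; that is a judgement, since neither document gives a frequency. The consequences are confined to consistent screening, the eligibility-violation listing and PPAS membership, and no bias in any result has been shown. The primary analysis, power and sample size do not change.

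The finding rests on the literal wording. It assumes that the sponsor did not mean to admit subjects above 10 mg/dL, which is the natural reading of a table of severe criteria.

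**What to change.** In Protocol section 8.3 item 3, and in the matching item of the synopsis, change the hepatic row to jaundice with bilirubin ≥ 8 mg/dL. The sponsor should confirm 8 mg/dL as the floor, because the documents give no source for either 8 or 10.

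SAP 11.4 and 13.4 need no edit, since they refer to the protocol criteria without repeating the threshold. The cost is one line in two places at the next protocol amendment, with no change to data collection or sample size.

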9. SUBJECT DISCONTINUATION, WITHDRAWAL AND TERMINATION FROM THE STUDY

9.1. Subject Discontinuation from Study Drug/Device

Vital status (whether alive or dead) will be determined on all subjects who prematurely discontinue. The specific reason for discontinuation will be documented. Subjects may be discontinued due to the following:

1. In the opinion of the Investigator, it is in the subject's best interests to discontinue study drug.
2. Subject no longer wishes to continue using the drug/device.
3. A subject becomes pregnant.
4. In the opinion of the Investigator, the subject experiences clinically significant rebound defined as clinically significant cardiopulmonary instability such as systemic arterial oxygen desaturation, hypoxemia, bradycardia, tachycardia, systemic hypotension, shortness of breath, near-syncope, and syncope occurring after acute withdrawal of study drug.
5. If methemoglobin $> 7\%$ is sustained or severe respiratory failure, multi-organ failure and/or other conditions arise that impair the ability of the subject to receive INOpulse, INOpulse therapy should be permanently discontinued.

9.2. Subject Withdrawal from Study

Subjects have the right to withdraw consent at any time and for any reason without prejudice to his/her future medical care by the physician or the institution. The specific reason for subject withdrawal of consent will be documented.

If the subject does not wish to continue study assessments, every effort should be made to obtain consent for contact of the subject, or the subject's family member or friends, to establish vital status.

In order to minimize the loss of data, it is critical all subjects are followed for 30 days post cessation of INOpulse therapy unless consent is withdrawn or a subject is lost to follow up.

If at any time, patient care decisions are made based upon resource limitations (eg, availability of PPE), the decision, date and reason should be documented.

9.3. Study Termination Criteria

The study may be terminated for any of the following reasons:

1. The local health authority requests a termination of the study.
2. It is determined that the risk level associated with the study drug/device combination therapy is significant and warrants termination of the study.
3. The Sponsor decides to terminate the study.

9.4. Deviations from the Protocol

A protocol deviation is defined as an event where the clinical Investigator or site personnel did not conduct the study according to the protocol or the Investigator Agreement. No deviations from the protocol should be initiated, except when necessary to eliminate immediate hazards to subjects (E6 ICH) and in accordance with FDA Guidelines on Conduct of Clinical Trials of Medical Products during COVID-19 Public Health Emergency.

10. TABLE 2: SCHEDULE OF ASSESSMENTS

Assessments	Screening	Baseline/ Randomization	On INOpulse (Up to Day 28) (Hospitalized)		Off INOpulse (Hospitalized)	Hospital Discharge* (if prior to End of Study)	If Discharged (Phone Call)	End of Study**	Early Discontinuation***
	0 to -14 days prior to Baseline	Day 0	Daily (Up to Day 27)	End of Treatment	Daily (Up to Day 28 or Day of Discharge if Earlier)	Day of Discharge	Day 7 Day 14 Day 28 (± 2 days)	30 Day Follow Up Post INOpulse completion (± 3 days)	If Applicable
Informed consent	X								
Medical History ¹⁰	X								
Review Eligibility Criteria	X	X							
Prior & Concomitant Medications ⁹	X	X	X	X	X	X	X	X	X
RT-PCR for COVID-19 ¹	X			X					X
Chest CT Scan or x-ray ⁴	X					X			X
Pregnancy Test (urine or serum)	X								
Vital signs ²	X	X	X	X					X
Methemoglobin ³		X	X	X					X
SpO ₂ via pulse oximetry ⁷ & O ₂ flow rate	X	X	X	X					X
Electrocardiogram (ECG)		X		X					X

Assessments	Screening	Baseline/ Randomization	On INOpulse (Up to Day 28) (Hospitalized)		Off INOpulse (Hospitalized)	Hospital Discharge* (if prior to End of Study)	If Discharged (Phone Call)	End of Study**	Early Discontinuation***
	0 to -14 days prior to Baseline	Day 0	Daily (Up to Day 27)	End of Treatment	Daily (Up to Day 28 or Day of Discharge if Earlier)	Day of Discharge	Day 7 Day 14 Day 28 (± 2 days)	30 Day Follow Up Post INOpulse completion (± 3 days)	If Applicable
Lab Evaluation ⁶	X			X					X
Physical Examination	X								
Clinical status using 8-point NIAID ordinal scale			X	X	X	X	X	X	X
Respiratory Failure Status				X	X	X	X	X	X
Monitor for pulmonary rebound for 1 hr post INOpulse discontinuation ⁸				X (upon INOpulse discontinuation)					X
INOpulse Device Set up & Dose Programming ⁵		X							
Drug Dispensing ⁵		X	X						
Download of INOpulse usage data				X					X
AE and SAE		X	X	X	X	X	X	X	X

¹ RT-PCR test for COVID-19 obtained from an upper respiratory tract specimen is required within 4 days of randomization. Another sample should be obtained from the nasopharynx or bilateral nares using a swab at End of Treatment. Subjects may be positive for COVID-19 or have high suspicion of infection at the time of randomization with RT-PCR results pending. If a subject is randomized based upon a high suspicion of COVID-19 infection and the swab RT-PCR comes back negative, a repeat RT-PCR swab can be taken and the

subject can be continued on INOpulse pending the repeat results. If the repeat RT-PCR results come back negative, the subject should be discontinued from INOpulse therapy. If the subject deteriorates after discontinuation of INOpulse, the Investigator should consider the reintroduction of INOpulse therapy

²Vital signs measured twice daily from Baseline until the last dose of INOpulse. Vital signs include heart rate, respiratory rate, blood pressure, and temperature. In the event an increase in O₂ flow rate is clinically indicated, SpO₂ should be monitored every 6 hours until stabilized. Document oxygen flow requirements.

³Methemoglobin assessed via Masimo RAD-57 (provided by Sponsor). Methemoglobin should be < 3% and SpO₂ >89% (with supplemental O₂ required) prior to continuing with treatment and should be monitored prior to, during the 1st hour (every ½ hour) and approximately 4-5 hours after initiation of INOpulse therapy. Thereafter, methemoglobin should be assessed twice daily (in conjunction with study drug cartridge changes) and remain ≤ 7 %. Otherwise, study drug should be discontinued.

⁴Chest x-ray or CT scan following onset of symptoms within 14 days prior to randomization and any time prior to discharge, as clinically indicated.

⁵Subjects will receive iNO125 mcg/kg IBW/hr or placebo for 24 hrs daily (until resolution of hypoxemia, protocol defined respiratory failure, discharge or Day 28 whichever occurs first.. In instances where continuous INOpulse dosing is not feasible (eg, due to PPE limitations), INOpulse should be used a minimum of 12 hours daily.

⁶Local lab tests to be done prior to start of study drug and at End of Treatment. Labs include CBC w/differential, chemistry panel (sodium, potassium, chloride, CO₂, BUN, creatinine, glucose), LFTs (AST/ALT and total bilirubin), troponin (High Sensitivity Cardiac Troponin [HS-cTN]), D-dimer, NT-pro-BNP (if NT-pro-BNP is not available locally, BNP can be drawn and converted using the online calculator: <https://www.cardio.med.tohoku.ac.jp/calc/nt-probnp.html>), LDH, fibrinogen, ferritin, triglycerides, pro-calcitonin. If available at the local lab, also include CRP, Von Willebrands Factor, Factor VIII Activity, Protein C, Protein S, Homocysteine, Antithrombin 3, Thrombelastography (TEG), G6PD deficiency and Prothrombin gene G2021A. Lab results obtained within the previous 48 hours of randomization are acceptable for screening purposes if there has not been a significant change in the subject's clinical status.

⁷Upon initiation of treatment, SpO₂ should be monitored to ensure levels are >89%. During INOpulse therapy, SpO₂ should be monitored twice daily to ensure levels are > 80%. In the event an increase in O₂ flow rate is clinically indicated, SpO₂ should be monitored every 6 hours until stabilized. Oxygen flow requirements should be documented throughout the study.

⁸Symptoms of pulmonary rebound include hypoxemia, bradycardia, tachycardia, systemic hypotension, shortness of breath, near-syncope and syncope. If signs or symptoms of rebound are observed, the INOpulse should be restarted and the Investigator should contact the Sponsor. SpO₂, BP and vital signs should be measured every 30 minutes for 1 hour.

⁹All prior and concomitant medications, including all over-the-counter medications and all current COVID-19 treatments (all therapies prescribed for the treatment of COVID-19

¹⁰Medical history to include the reason for hospital admission.

*Complete Hospital Discharge Assessments only if it occurs before the End of Study. Otherwise, if the subject is still in hospital at the time of End of Study (30 day follow up post INOpulse completion), complete only the End of Study assessments indicated.

**Subjects will be assessed via telephone if discharged from the hospital. The assessments are to be performed in person, in the unlikely event the subject is still hospitalized.

***Early Discontinuation if methemoglobin > 7% is sustained or severe respiratory failure, multi-organ failure and/or other conditions arise that impair the ability of the subject to receive INOpulse, INOpulse therapy should be permanently discontinued. Severe respiratory failure does not include subjects that require use of High Flow Nasal Cannula ≤ 15L/minute (these subjects can continue to receive INOpulse treatment). It is critical early discontinuation subjects are followed for 30 days following last INOpulse therapy. This does not include if subjects withdraws consent or is lost to follow up.

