- CBC with differential, chemistry panel (sodium, potassium, chloride, CO₂, BUN, creatinine, glucose), LFTs (AST/ALT and total bilirubin), triglycerides, troponin (High Sensitivity Cardiac Troponin [HS-cTN], procalcitonin, ferritin, fibrinogen, D-dimer, NT-proBNP and LDH. If available locally, CRP, Von Willebrands Factor, Factor VIII Activity, Protein C, Protein S, Homocysteine, Antithrombin 3, Thrombelastography (TEG), G6PD deficiency and Prothrombin gene G2021A
- COVID-19 RT-PCR obtained by nasopharyngeal or bilateral nasal swab
- Review of prior and concomitant medications, that includes all current COVID-19 treatments (all therapies prescribed for the treatment of COVID-19)

- Electrocardiogram (ECG)
- Vital signs, methemoglobin and oxygen saturations
- Oxygen flow requirements
- Respiratory Failure Status
- Clinical status using an 8-point NIAID ordinal scale (**Table 1**)
- Upon discontinuation of INOpulse, irrespective of reason, subjects should be monitored for 1 hour for symptoms of pulmonary rebound which include hypoxemia, bradycardia, tachycardia, systemic hypotension, shortness of breath, near-syncope, and syncope. SpO₂, BP and vital signs should be measured every 30 minutes for 1 hour.
- Adverse event(s) assessment
- Download usage data from the INOpulse device

If at any time, patient care decisions are made based upon resource limitations (eg, availability of PPE), the decision, date and reason should be documented.

Criteria for Study Drug Interruption: If methemoglobin >7%, SpO₂ falls below 80%, or clinically significant INOpulse-related adverse events are observed, INOpulse therapy should be interrupted. INOpulse therapy may be re-started at the discretion of the Investigator.

Criteria for Study Drug Discontinuation: If methemoglobin > 7% is sustained or severe respiratory failure, multi-organ failure and/or other conditions arise that impair the ability of the subject to receive INOpulse, INOpulse therapy should be permanently discontinued. Severe respiratory failure does not include subjects who require use of High Flow Nasal Cannula (HFNC) ≤ 15 L/minute (these subjects can continue to receive INOpulse treatment).

In order to minimize the loss of data, it is critical all subjects are followed for 30 days post cessation of INOpulse therapy unless consent is withdrawn or a subject is lost to follow up.

Number of subjects and sites:

Multi-center study enrolling approximately 500 subjects at approximately 30 sites.

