10.1.12. Methemoglobin

Methemoglobin will be assessed prior to initiating INOpulse, during the 1st hour (every ½ hour) of the first dose of INOpulse and approximately 4-5 hours after initiating INOpulse therapy. Methemoglobin should be < 3% and SpO₂ >89% (with supplemental O₂ required) prior to continuing with treatment.

Following initiation of treatment, methemoglobin will be assessed twice daily while on INOpulse. Levels should not exceed >7%, otherwise the study drug should be interrupted and/or discontinued.

Sponsor will provide Masimo RAD-57 with rainbow probe to monitor methemoglobin in subjects treated with INOpulse.

Criteria for Study Drug Interruption: If methemoglobin exceeds 7%, SpO₂ falls below 80%, or clinically significant iNO-related adverse events are observed, INOpulse therapy should be interrupted. INOpulse therapy may be re-started at the discretion of the Investigator.

Criteria for Study Drug Discontinuation: If methemoglobin > 7% is sustained or severe respiratory failure, multi-organ failure and/or other conditions arise that impair the ability of the subject to receive INOpulse, INOpulse therapy should be permanently discontinued. Severe respiratory failure does not include subjects that require use of High Flow Nasal Cannula \leq 15L/minute (these subjects can continue to receive INOpulse treatment).

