10.1.14. Symptomatic Rebound Testing Post INOpulse Discontinuation

Subjects receiving INOpulse should be monitored every 30 minutes for 1 hour after discontinuation of treatment, including early discontinuation subjects, for signs and symptoms of rebound (eg, systemic arterial oxygen desaturation, hypoxemia, bradycardia, tachycardia, systemic hypotension, shortness of breath, near-syncope, and syncope). If symptomatic rebound is observed, treatment with INOpulse should be re-started and the Investigator should contact Bellerophon.

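### The protocol gives two instructions for a methemoglobin reading above 7% that is not sustained, and leaves its rebound instructions unreconciled; either can change how the descriptive safety endpoint is coded

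*Protocol*

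**What the plan says.** **Methemoglobin above 7%.** Protocol Table 2, footnote 3, requires levels to remain at or below 7% once treatment is under way, and adds: "Otherwise, study drug should be discontinued". It has no interruption step and does not ask whether the level persists. The synopsis lists methemoglobin above 7% among its interruption criteria, in a sentence that ends "clinically significant INOpulse-related adverse events are observed, INOpulse therapy should be interrupted", and leaves restart to the investigator. Section 10.1.12 sets the same criteria: "INOpulse therapy should be interrupted. INOpulse therapy may be re-started at the discretion of the Investigator". Section 10.1.12 also contains a hybrid sentence: "Levels should not exceed >7%, otherwise the study drug should be interrupted and/or discontinued". Permanent discontinuation is tied to a sustained level in the synopsis, in section 9.1 item 5, in section 10.1.12 and in footnote *** of Table 2 ("Early Discontinuation if methemoglobin > 7% is sustained").

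**Rebound.** Section 9.1 lists reasons for which subjects may be discontinued. Item 4 applies when, in the investigator's opinion, "the subject experiences clinically significant rebound defined as clinically significant cardiopulmonary instability" after acute withdrawal of drug. Section 10.1.14 says: "If symptomatic rebound is observed, treatment with INOpulse should be re-started", and its monitoring explicitly covers subjects who discontinue early. Table 2 footnote 8 gives the same restart instruction.

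**Safety endpoint.** Protocol 7.3 and SAP 9.0 name one: the proportion of subjects with an adverse event that leads to stopping study drug by Day 28. SAP 13.6.2 identifies such events by the recorded action, Drug Withdrawn. SAP 13.6 says the proportion will be displayed overall and by arm, and words it as discontinuation from the study rather than from study drug.

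**The concern.** A rule for stopping study drug should read the same wherever a site looks it up. Here a site that follows footnote 3 and a site that follows section 10.1.12 could both claim to follow the protocol and yet handle the same reading differently: one ends treatment, the other pauses it and may resume. For rebound, one passage offers discontinuation and two others direct a restart, and nothing says when each applies.

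Two things are at stake. The first is subject safety, because these are instructions about stopping and resuming an investigational gas. The second is measurement. The only endpoint listed for the safety objective turns on whether drug was withdrawn, and that is the classification on which the passages differ.

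**Working it through.** The plan states no figure on this point, so the check is a comparison of passages, followed by a note on scale.

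**1. Methemoglobin, by case.**

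| Case | Table 2 footnote 3 | Synopsis and 10.1.12 | 9.1 item 5 and footnote *** |
|---|---|---|---|
| Above 7%, not sustained | Discontinue | Interrupt; restart at investigator's discretion | Not triggered |
| Above 7%, sustained | Discontinue | Permanently discontinue | Permanently discontinue |

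The second row is consistent. The conflict is in the first row, and the line between the rows depends on the word *sustained*, for which the protocol gives no duration or number of readings. After the first day, readings are scheduled twice daily. The hybrid sentence in 10.1.12 allows either action and does not settle the matter. Footnotes 3 and *** belong to the same table.

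**2. Rebound.**

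| Source | Trigger | Force | Action |
|---|---|---|---|
| 9.1 item 4 | Clinically significant rebound, investigator's opinion | May | Discontinue |
| Table 2 footnote 8 | Signs or symptoms of rebound | Should | Restart |
| 10.1.14 | Symptomatic rebound, including after early discontinuation | Should | Restart |

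The symptom lists largely coincide. By the definition in 9.1, rebound follows withdrawal of drug, so item 4 gives as a reason to stop an event that occurs once drug is already off.

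**3. Where the two topics meet.** Footnote *** says therapy should be permanently discontinued in, among others, subjects with sustained methemoglobin above 7%. Table 2 marks rebound monitoring in the Early Discontinuation column, and 10.1.14 applies its restart instruction to those subjects. A subject stopped under footnote *** who then shows rebound therefore falls under both permanent discontinuation and restart, with no exception stated.

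**4. Route to the endpoint.** An event counts only if it is recorded as an adverse event and the action taken is Drug Withdrawn (SAP 13.6.2). Protocol 13.4.1 limits adverse-event entry of laboratory results to those that qualify as adverse events. SAP 13.6.2 lists methemoglobin at or above 7.0% and rebound symptoms as events of special interest. That makes recording likely but does not fix the action taken. Neither document says how to code an interruption followed by restart, or rebound after drug is already off. Two thresholds also differ between documents: above 7% in the protocol against 7.0% or more in the SAP, and one hour of rebound monitoring against a 20-minute window.

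**5. Scale.** SAP 8.1 plans 500 subjects at 1:1, so 500 / 2 = 250 per arm, assuming all are treated. One subject recoded between interrupted and withdrawn moves that arm by 1/250 = 0.4 percentage points; an assumed five subjects, by 5/250 = 2.0 points. The only prior data are 25 expanded-access patients with no level above 1.5% (protocol section 5). With 0 of 25, the exact one-sided 95% upper limit for the rate of readings above 1.5% is 1 − 0.05^(1/25) = 11.3%. The rate above 7% cannot be derived from this.

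**The case against.** The best defence is that footnote 3 is a lone outlier. Four other places make permanent discontinuation depend on a sustained level, one of them in the same table. Footnote 3 also does not say that discontinuation is permanent, and footnote 1 uses the same verb for negative RT-PCR subjects while allowing therapy to be reintroduced. On any reading, drug stops when the level exceeds 7%; the passages differ only on whether it may resume. This softens the conflict but does not remove it, because footnote 3 gives neither the interruption step nor the permission to restart.

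A reader might infer opposite orders on rebound. The text does not go that far. Section 9.1 is permissive and limited to clinically significant rebound in the investigator's opinion, and a restart followed later by a decision to end therapy is a possible sequence. What stands is that no sequence is stated, and that the restart instruction meets permanent discontinuation under footnote ***.

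A reader might also infer that every reading above 7% and every rebound event is affected. Sustained readings are handled consistently, and rebound not judged clinically significant never meets item 4 of section 9.1. Nor do the documents show that sites will divide according to the page they consult.

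Finally, a reader might infer that the safety conclusion depends on this. The endpoint is displayed by arm without a test, and the gatekeeping in SAP 13.5.2 covers only the primary and secondary efficacy endpoints. Methemoglobin results, device usage and drug discontinuations are listed by subject, and an unblinded monitoring committee reviews data at least monthly. These are real safeguards, but Appendix 4 tabulates discontinuations and has no table of interruptions.

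**Conclusion.** The point holds in a limited form. The protocol conflicts for methemoglobin above 7% that is not sustained, and the boundary term is undefined. Its rebound passages are unreconciled: discontinuation is permitted in one place and restart is directed in two others, including for subjects who have been permanently discontinued.

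These differences can change whether an adverse event is coded Drug Withdrawn, and so the safety proportion, but only in subjects who have such events and have them recorded as adverse events. How many that would be cannot be derived. The 0.4 points per subject rests on 250 treated per arm and is a scale, not an estimate of impact. The primary efficacy analysis and error control are not affected. Rarity would limit the statistical effect, but it does not remove the need for one instruction on stopping and resuming study drug. No view is taken here on which instruction is clinically right.

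**What to change.** In the protocol, the sponsor must:

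- reconcile Table 2 footnote 3 with the synopsis, section 9.1 item 5, section 10.1.12 and footnote ***, and say what *sustained* means;
- reconcile section 9.1 item 4 and footnote *** with footnote 8 and section 10.1.14, so that each trigger has one instruction, including for subjects who stopped early.

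In the SAP, state how interruption, restart and rebound after withdrawal are coded for the safety endpoint. While section 13.6 is open, align its wording with the study-drug discontinuation named in protocol 7.3.

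The cost is a protocol clarification and a few lines of SAP text. Tabulating temporary interruptions separately from permanent withdrawals by arm would be a useful but optional extra row.
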